11.2.2 Safety analysis and stopping rules

During the recruitment phase of the trial, safety analyses will be conducted to determine whether subject accrual to each cohort should continue or cease. Cessation of subject accrual will occur if an unacceptable rate of ipsilateral invasive recurrence is detected. Safety analyses will be performed on the two HER2 cohorts (positive and negative) and in two cohorts of participants based on tumour grade (high grade and non-high grade). In the first 46 participants in each cohort, a 7% IIRR would require no ipsilateral invasive recurrences while one ipsilateral invasive recurrence would be consistent with up to a 10% event rate (with 95% confidence). During the early part of recruitment each local recurrence will have a large effect on the IIRR confidence limits than a recurrence during the latter part of recruitment. For example, in the HER2 negative cohort, if one ipsilateral invasive recurrence is observed in the first 10 participants but no other ipsilateral invasive recurrences occur in the subsequent 150 participants enrolled, overly restrictive stopping rules would result in premature and

unnecessary closure of accrual. Therefore, it is thought that stopping the study after one ipsilateral invasive recurrence in the first 46 participants would be premature to adequately address the scientific question. So for the first 46 participants, a 10% recurrence rate boundary is appropriate. Thus, if 2 or more local recurrences occur in the first 46 participants in each cohort, accrual to that particular cohort will cease. Similarly, if 3 or more ipsilateral invasive recurrences are observed in the first 90 participants in each cohort, accrual to that particular cohort will cease. For 90, 110, 130 and 150 participants the boundaries (see Tables 3 and 4) assume a IIRR in the HER2 negative population consistent with 7% or lower.

Due to the lower expected number of HER2 positive participants, accrual of participants who are HER2 positive will be stopped if at any time the cumulative number of ipsilateral invasive recurrences observed in the 5 year period exceeds 1, i.e. 2 or more ipsilateral invasive recurrences are observed. In the event that the accrual of HER2 positive participants is higher than anticipated, accrual to this cohort will proceed to 50 participants to allow for increased precision of IIRR. The rules for stopping accrual continue to apply so that if at any time the number of ipsilateral invasive recurrences exceeds 1, then accrual to the HER2 positive cohort will cease.

As 2 ipsilateral invasive recurrences are the first threshold for possible cessation of subject accrual, safety analysis and a decision on continuing or ceasing subject accrual will occur at the time of detection of the second local recurrence and at the time of all further ipsilateral invasive recurrences.

The following tables give the number of ipsilateral invasive recurrences required to rule out a $\geq 10\%$ rate up to 46 participants and after 46 participants, a $\geq 7\%$ rate.

Table 3 Stopping rules for HER2+ and HER2- cohorts

Rules for stopping accrual based on the number of ipsilateral invasive recurrences observed in HER2+ and HER2- cohorts:

Number of participants accrued in each cohort						
	Any	46	90	110	130	150
HER2+	≥ 2	-	-	-	-	-
HER2-	-	$\geq 2^*$	$\geq 3^\ddagger$	$\geq 4^\ddagger$	$\geq 5^\ddagger$	$\geq 6^\ddagger$

*Unacceptable IIRR of 10% is consistent with this result

‡ Unacceptable IIRR of 7% is consistent with this result

Table 4 Stopping rules for high grade and non-high grade cohorts

Rules for stopping accrual based on the number of ipsilateral invasive recurrences observed in high grade and non-high grade cohorts:

Number of participants accrued in each cohort						
	46	90	110	130	150	
High grade	≥2*	≥3‡	≥4‡	≥5‡	≥6‡	
Non-high grade	≥2*	≥3‡	≥4‡	≥5‡	≥6‡	

*Unacceptable IIRR of 10% is consistent with this result

‡ Unacceptable IIRR of 7% is consistent with this result

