11.2 Study endpoints and Data Analyses

11.2.1 Analysis of the primary endpoint

The primary analysis will include all registered patients.

Primary endpoint:

- Ipsilateral invasive recurrence rate (IIR) in the breast at 5 years follow up from the date of definitive excisional surgery.

It is considered that a IIRR of 5% at 5 years would be acceptable, while a IIRR of >7% at 5 years would mean that the hypothesis is not supported.

Based on these numbers, the objective is to estimate the IIRR in participants with low risk breast cancer who do not receive radiotherapy. An estimate of an overall IIRR of 5% would be clinically acceptable and based on 200 participants; this would have 90% chance of declaring a true recurrence rate of <7%. The expected number of participants who are HER2 positive to be recruited is 30-35. The expected number of participants who are HER2 negative to be recruited is 165-170. The sample size for this study is 200 registered participants. The main efficacy analysis is planned after the 100th registered subject has reached 5 years of follow up. Efficacy data will also be reviewed after the 100th registered subject has reached 2 years of follow up.

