11.2.5 Accrual rate

Average of 22 patients per year over 9 years.

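### The accrual-stopping boundaries are limits for complete 5-year follow-up applied to numbers merely accrued, so staying under them does not rule out a 10% or 7% IIRR

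*Protocol*

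**What the plan says.** Section 11.2.1 defines the rate of interest at 5 years: "It is considered that a IIRR of 5% at 5 years would be acceptable, while a IIRR of >7% at 5 years" would not support the hypothesis. Section 11.2.2 sets rules, operating during recruitment, for closing accrual to cohorts defined by HER2 status and by grade. For the first stage it reasons that a single event among 46 participants "one ipsilateral invasive recurrence would be consistent with up to a 10% event rate (with 95% confidence") is tolerable, having noted that the 7% limit would need zero events at that size. It adopts the 10% limit for that stage and a 7% limit at 90, 110, 130 and 150.

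Tables 3 and 4 stop accrual at 2, 3, 4, 5 and 6 or more events at those five sizes, so the allowed counts are 1, 2, 3, 4 and 5. The column heading is "Number of participants accrued in each cohort". The lead-in is "The following tables give the number of ipsilateral invasive recurrences required to rule out a" rate of at least 10% up to 46 participants and at least 7% thereafter. The decision is taken when the second and each later recurrence is detected. The section gives no minimum follow-up and no person-time basis. Section 11.2.5 plans accrual as "Average of 22 patients per year over 9 years".

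The HER2-positive cohort has its own rule: stop at 2 or more events at any time.

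**The concern.** A binomial limit for a 5-year rate needs a 5-year outcome for each person in the denominator. Someone who joined last month adds one to the number accrued and almost nothing to the chance of seeing a recurrence. A count that would exclude 10% among 46 women followed for 5 years therefore excludes far less among 46 women recruited over the previous two and a half years.

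These are the protocol's only numerical stopping boundaries for women who forgo radiotherapy, and a stated confidence is attached to them. If that confidence is wrong, an uncrossed boundary could be taken by the monitoring committee, or in a report, as showing that 10% or 7% had been excluded when it had not.

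**Working it through.** **1. Reproduce the plan's figures.** The one-sided exact 95% upper limit for x events in n is the 0.95 quantile of Beta(x+1, n−x):

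- 0/46 = 6.3% and 1/46 = 9.9%
- 2/90 = 6.8%
- 3/110, 4/130 and 5/150 = 6.9% each

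All five boundaries reproduce, as does the remark about zero events in 46. Two-sided limits do not: 11.5%, 7.8%, 7.8%, 7.7% and 7.6%. The construction is therefore one-sided, with every participant counted as fully followed.

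**2. Follow-up actually present.** Inputs: 165–170 HER2-negative participants expected (section 11.2.1; 167 used) over 9 years (section 11.2.5), so a = 167/9 = 18.56 per year. Assumptions: evenly spaced entry and constant hazard. Participant i enters at i/a years and contributes at most 5 years.

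- n = 46 is reached at 46/18.56 = 2.48 years. Person-years = 46×45/(2×18.56) = 55.8, a mean of 1.2 years each.
- n = 90 is reached at 4.85 years, so nobody yet has 5 years. Person-years = 90×89/(2×18.56) = 215.8.
- For n = 110, 130 and 150 the 5-year cap applies. Person-years = 5n − 12.5a − 2.5 = 5n − 234.4, giving 315.6, 415.6 and 515.6.

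**3. Upper limits at the allowed counts.** Divide the one-sided 95% Poisson bound for x events by the person-years, then convert by 1 − exp(−5 × rate). For 46: 4.744/55.8 = 0.0850 per year, and 1 − exp(−0.425) = 34.6%.

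**4. Chance of being under each boundary when the true 5-year rate is the one said to be excluded.** The hazard is −ln(0.90)/5 = 0.02107 for 10% and −ln(0.93)/5 = 0.01451 for 7%. Each participant's event probability is 1 − exp(−hazard × follow-up), and these are combined exactly. Hand check at 46: expected events 0.02107 × 55.8 = 1.18, and the Poisson chance of 0 or 1 is about 67%.

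| Accrued | Share of full 5-year person-time | Allowed events | Poisson bound | Limit as planned | Limit given follow-up | Chance under boundary (true rate) | Chance with complete follow-up |
|---|---|---|---|---|---|---|---|
| 46 | 24% | 1 | 4.74 | 9.9% | 35% | 68% (10%) | 4.8% |
| 90 | 48% | 2 | 6.30 | 6.8% | 13.6% | 40% (7%) | 4.4% |
| 110 | 57% | 3 | 7.75 | 6.9% | 11.6% | 34% (7%) | 4.6% |
| 130 | 64% | 4 | 9.15 | 6.9% | 10.4% | 30% (7%) | 4.6% |
| 150 | 69% | 5 | 10.51 | 6.9% | 9.7% | 26% (7%) | 4.5% |

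**5. Sensitivity.**

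- Later recurrences (Weibull shape 1.5): 86–87% at 46, and 33–57% at 90 to 150.
- Accrual over 8 years: limit 37% at 46, and a 72% chance that a true-10% cohort is under that boundary.
- Accrual of only 5 per year: 14% at 46 and 8–9% at 90 to 150, still above 5%.

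**6. The rule in sequence** (simulation, constant hazard). By 150 accrued it stops a true-7% cohort about 83–84% of the time, so such a cohort passes the whole sequence 16–17% of the time. Checked at each event to the end of accrual, with 6 or more still the threshold beyond 150, it stops a true-10% cohort about 99% of the time, a true-7% cohort about 89%, and a cohort at the acceptable 5% about 65%.

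**7. HER2-positive.** One event is allowed in an expected 30–35 participants. Even with complete follow-up the limit is 14.9% (1/30) to 12.9% (1/35).

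**The case against.** The strongest reply is that the single-look percentages misdescribe how the rule works. The boundaries act one after another, at every recurrence from the second, and taken together they stop most cohorts with an unacceptable rate. That stands. A reader might infer from 68% at the first boundary that the rule is lax, but the sequential results contradict this. If anything it often closes an acceptable cohort.

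A reader might also infer that the tables are the only protection. They are not. Section 10.2 has the monitoring committee review the local recurrence rate every six months, section 11.2.1 adds a review when the 100th participant reaches 2 years, and section 6.1.6 requires an 18-month MRI and reporting of suspected recurrence within 24 hours.

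It is tempting to say that the protocol claims 10% is excluded for HER2-positive women. Table 3 does not clearly say so: that cell carries neither footnote, and only the general lead-in sentence could reach it.

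The first 46 participants could perhaps mean 46 women each followed for 5 years, which would make the limits right. The column heading, the restriction to recruitment and the decision at detection all tell against that reading.

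Finally, the adjusted limits depend on constant hazard and even accrual, which the protocol does not fix, and the grade cohorts in Table 4 have no stated size, so they were not computed. This affects the size of the discrepancy. Its direction held in every sensitivity case run.

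**Conclusion.** The concern holds for the stated confidence property. The 10% and 7% limits are correct for complete 5-year follow-up and wrong for numbers accrued during recruitment, so the rule-out statement is false as written. For the HER2-negative cohort, under the working assumptions, the real limits run from about 35% at 46 accrued to 9.7% at 150. At a single look, a cohort at the rate supposedly excluded is under the boundary 26–68% of the time, against a nominal 5% or slightly less.

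The finding does not extend to the stopping rule as a safeguard, and it does not show that the thresholds should change. Appendix K reports 201 participants allocated against a target of 200 and a primary analysis already done, so no accrual decision appears to remain. What is left is how the boundaries are described and reported. Appendix K's ipsilateral events, at 4.5, 6.5 and 7.5 years, illustrate why counts taken early in follow-up say little about a 5-year rate.

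A smaller inconsistency sits in the same section: one sentence stops accrual "if 2 or more local recurrences occur in the first 46 participants", while the tables count ipsilateral invasive recurrences. Ipsilateral DCIS recurrence is a separate endpoint (section 11.3.2), so the two terms need not give the same count.

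**What to change.** In section 11.2.2:

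- State that the limits for 46, 90, 110, 130 and 150 assume a 5-year outcome for every participant counted.
- Delete the rule-out and 95% confidence claims where the denominator is participants accrued. In their place give person-time limits as in the table above, with their assumptions, or the estimated cumulative incidence with its confidence limit.
- State that the rule-out sentence does not cover the HER2-positive rule, where one event in 30–35 has an upper limit of 14.9–12.9% even with complete follow-up.
- Reconcile local recurrence with ipsilateral invasive recurrence as the trigger term.

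In reports, do not offer uncrossed boundaries as evidence that 7% or 10% was excluded. Leave that question to the 5-year endpoint analysis.

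Do not re-index Tables 3 and 4 by 5-year equivalents. That would change the stopping rule: in simulation a true-5% cohort would be stopped about 90% of the time against about 65% now, and a true-3% cohort about 62% against 26%. With accrual complete it would also serve no purpose.

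The cost is statistician time and wording, with no new data. The downside is that the stated assurance becomes weaker.

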11.2.3 Analysis of the Secondary Endpoints

Secondary endpoints:

1. Ipsilateral invasive recurrence rate in the breast at 10 years
2. Ipsilateral DCIS recurrence rate in the breast at 5 and 10 years
3. Regional recurrence rate at 5 and 10 years
4. Distant recurrence rate at 5 and 10 years
5. Contralateral breast cancer rate at 5 and 10 years
6. Breast-cancer specific survival rate at 5 and 10 years
7. Overall survival rate at 5 and 10 years

Analysis of ipsilateral invasive recurrence will also be performed when the 100th subject enrolled reaches 10 years of follow up from the date of definitive excisional surgery. Regional and distant recurrence rate will be analysed when the 100th subject enrolled reaches 5 years and 10 years of follow up from the date of definitive excisional surgery. Time to event outcomes (breast cancer specific and overall survival at 5 and 10 years) will be described using Kaplan Meier curves. The potential impact of baseline factors on recurrence and time to recurrence will be examined using appropriate regression methods (logistic, proportional hazards).

11.2.4 Other descriptive analyses

The entire cohort of patients undergoing pre-operative staging MRI will be included in descriptive analyses of:

- A substudy of the outcome of MRI at breast cancer diagnosis, the impact of MRI and the accuracy of MRI (Appendix H).

- An economic evaluation to determine the potential cost-effectiveness of implementing a protocol where women with cT1cN0 hormone receptor-positive and/or HER2 positive early stage breast cancer undergo a pre-surgical MRI (and for those women where the MRI clearly shows no synchronous cancer lesions radiotherapy is omitted) compared to standard practice (no MRI and all women receive radiotherapy (Appendix I).
- A substudy of outcomes of the patients who underwent MRI but were deemed unsuitable for inclusion in the main study who consent to follow up (Appendix J).
- A substudy (Appendix K) to:
 - Conduct sequencing of the index and subsequent lesions to determine whether they are true recurrences or whether they are independent lesions
 - Analysis of the index lesion where there has been a subsequent event using the PAM50 assay, to determine whether it may identify those at high risk of recurrence.

11.2.5 Accrual rate

Average of 22 patients per year over 9 years.

11.3 Ipsilateral invasive, ipsilateral DCIS, regional, distant recurrence definitions

The date that a suspicious ipsilateral invasive, ipsilateral DCIS, regional or distant breast cancer recurrence is first suspected and the date that a recurrence is confirmed (per the “acceptable” criteria listed below) will be collected to define and analyse the primary and secondary endpoints.

11.3.1 Ipsilateral invasive recurrence

Ipsilateral invasive recurrence is defined as an invasive recurrence (with or without in-situ tumour) in any soft tissue of the ipsilateral conserved breast or skin.

- Acceptable for recurrence in ipsilateral conserved breast: positive histology.
- Acceptable for recurrence in skin: positive histology
- Suspicious: positive cytology or a visible or palpable lesion.

The diagnosis of LCIS either in the ipsilateral breast or in the contralateral breast is not considered an endpoint for this trial, but should be reported on the case record form.

11.3.2 Ipsilateral DCIS Recurrence

Ipsilateral DCIS recurrence is defined as the diagnosis of any DCIS occurrence (without associated invasive carcinoma) in any soft tissue of the ipsilateral conserved breast.

- Acceptable for diagnosis of DCIS in ipsilateral conserved breast: positive histology.
- Suspicious: suspicious mammographic or MRI findings.

11.3.3 Regional Recurrence

Regional recurrence is defined as a tumour recurrence in the ipsilateral axillary lymph nodes, extranodal soft tissue of the ipsilateral axilla, ipsilateral internal mammary lymph

nodes, and/or ipsilateral supraclavicular lymph nodes. Regional recurrence does not include supraclavicular lymph nodes or tumour in the opposite breast (see section 11.3.4 for information on contralateral breast cancer).

- Acceptable: positive cytology or histology
- Suspicious: a visible or palpable lesion or evidence of new lesions by CT or MRI without a benign aetiology

11.3.4 Distant Recurrence

Recurrence in all areas other than those defined above are considered distant metastases. The following criteria apply:

11.3.4.1 Bone marrow

- Acceptable: positive cytology or histology.
- Suspicious: unexplained depression of peripheral blood counts and/or a leucoerythroblastic blood picture.

11.3.4.2 Lung

- Acceptable: positive cytology or histology, or a positive CT or MRI without obvious benign aetiology, or evidence of progressive disease. (Progressive disease is confirmed by two X-rays with the second showing worsening disease.)
- Suspicious: new radiological lesion(s).

11.3.4.3 Pleura

- Acceptable: positive cytology or histology.
- Suspicious: new pleural effusion.

11.3.4.4 Bone

- Acceptable: positive cytology or histology or a positive X-ray, MRI, or CT or bone scan with new multiple lesions and no obvious benign aetiology.
- Suspicious: skeletal symptoms or positive scan showing only one new lesion (until confirmed by other imaging study or biopsy).

11.3.4.5 Liver

- Acceptable: positive cytology or histology, or positive CT or MRI without an obvious benign aetiology, or evidence of progressive disease by ultrasound or CT. (Progressive disease in this case is confirmed by two ultrasounds or CTs with the second showing worsening disease.)
- Suspicious: any two of the following: hepatomegaly on physical examination, equivocal ultrasound and abnormal liver function test.

11.3.4.6 Central nervous system

- Acceptable: positive cytology or histology. Positive MRI or CT when the clinical picture is suspicious.
- Suspicious: any other clinical findings suggestive of this diagnosis.

11.3.4.7 Distant lymph nodes

- Acceptable: positive cytology or histology
- Suspicious: evidence of enlarged lymph nodes by physical exam, or enlarged lymph nodes in CT or MRI, or progressive disease by physical exam without an obvious benign aetiology.

11.3.4.8 Other sites

- Acceptable: positive cytology or histology or evidence of progressive disease if only indirect means of diagnosis were used (e.g., X-ray).
- Suspicious: clinical and radiological evidence of a tumour.

11.3.5 Contralateral breast cancer

The first contralateral invasive breast cancer must be reported on the SPM form if it occurs at any time during the study

- Acceptable: positive cytology or histology.
- Suspicious: a visible or palpable lesion, suspicious mammogram, ultrasound, or MRI.

The diagnosis of LCIS and DCIS in the contralateral breast is not considered an endpoint for this trial, but should be recorded on the case record form.

11.4 Second (non-breast) primary

Any positive diagnosis of a second (non-breast) malignancy other than a basal cell or squamous cell carcinoma of the skin, cervical carcinoma in situ, or bladder cancer in situ should be reported on the case record form (SPM).

11.5 Death

All deaths must be reported. The date and cause of death must be reported on the case record form (DR).

12 ETHICAL AND REGULATORY CONSIDERATIONS

12.1 Required Documents

Prior to initiating this trial, the Principal Investigator at each institution will ensure that all required regulatory and other associated documentation is forwarded to BCT.

12.1.1 Submission of Regulatory Documents

All regulatory documents are to be submitted to BCT. Once BCT has received complete and accurate documents from a participating institution, the institution will be activated to commence pre-registration and registration of patients.

12.2 Human Research Ethics Committee (HREC)

All protocols and the Participant Information Sheet and Consent Forms must have the approval of a properly constituted ethics committee. The approving HREC must provide a written, signed letter/form which must specify approval for the designated investigator, the trial protocol (identifying protocol title and version date), and of the Participant Information Sheet and Consent Form (identifying version date). Additionally, all recruitment materials must be reviewed by the approving HREC. Documentation of ethics committee approval must be sent to the BCT.

The Principal Investigator (or Coordinating Investigator for multi-centre ethics submissions) is responsible for informing the approving HREC of any amendment to the protocol.

The Principal Investigator (or Coordinating Investigator) must submit progress reports to the HREC according to the committee regulations and guidelines. The approving HREC must also be notified of all reports of SAEs from the trial centres.

12.3 Informed Consent

The Participant Information Sheet and Consent Forms (screening and main) must be reviewed and approved by BCT and the approving HREC prior to trial initiation. For multi-centre ethics submissions, the lead HREC will review the template Participant Information Sheet and Consent Forms. Any subsequent changes to these documents (other than local site identifiers) must be approved by BCT prior to submission to the HREC. Template Participant Information and Consent Forms are provided in Appendix A.

Informed consent from each patient must be obtained prior to initiating any trial procedures in accordance with the International Conference on Harmonisation for Good Clinical Practice (ICH-GCP). All potential trial participants will be given a copy of the HREC approved Participant Information Sheet and Consent Forms to read and discuss with family, GP etc. The investigator will explain all aspects of the trial in lay language and answer all questions regarding the trial.

If the patient decides to participate in the trial, she will be asked to sign the Informed Consent documents (screening initially and if eligible following screening then the

main). One copy of the Participant Information Sheet and signed Informed Consent must be given to the patient to keep and one copy must be retained in the institutional Investigator File. The completed and signed Informed Consent documents for all patients at the institution must be available in the case of data audits. Patients who refuse to participate or who withdraw from the trial will be treated without prejudice.

Regarding the substudy of outcomes of the patients who underwent MRI but were deemed unsuitable for inclusion in the main study, patients will be asked to sign the relevant Informed Consent document. Those patients who refuse consent, or decline to complete the consent, will not have additional information included, beyond the details collected as part of the screening aspect of the study to which they have already consented. They will be reported as 'refused consent' for this additional information.

A request to waive consent will be submitted to HREC for those patients who have died in the intervening time, those who are unable to provide informed consent due to mental deterioration and for those who are unable to be contacted. For these patients, information available within the medical records will be used in the study.

